Our objective is to develop personalized treatment approaches to the treatment of acute HF. The central hypothesis is that BVA will allow improved congestion phenotyping of acute HF patients given the ability to directly and accurately measure blood volume. Knowledge of specific congestion phenotypes will be the basis for targeted treatment algorithms. **The specific objectives are:**

Perform a pragmatic randomized pilot study (N=50) with blood volume analysis (BVA) – guided treatment strategy vs standard of care in patients admitted for acute decompensated HF *A*: Study effects of unblinded BVA results on provider treatment choices and clinical endpoints *B*: Develop a new BVA-guided treatment algorithm based on the observed experience with BVA at Duke

4. Design & Procedures

Perform a pragmatic randomized pilot study (N=50) with BVA- guided treatment strategy vs standard of care in patients admitted for acute decompensated HF.

The main intent for this pilot study is to gather information on optimal study design, treatment recommendations and sample size for a future planned pivotal trial.

Design: Pragmatic pilot study of patients admitted with acute HF. Upon enrollment patients will be randomized to either the unblinded arm (BVA- guided treatment), or blinded arm (Standard of care treatment), where BVA results will not be provided to patients or provider team. The study is planned to start in the Spring, 2020 and be open for enrollment for 1 year. (**Figure 2**)

Population: Patients presenting to Duke Hospital with a history of HF and worsening symptoms of HF will be enrolled in the study. Exclusion criteria are: Ongoing pregnancy, age <18 years, post heart transplantation or ongoing mechanical circulatory support, and end stage renal disease.

Treatment protocol: A pre-determined assortment of demographic and medical information will be gathered for all patients upon admission, 24h, 48h, 72h and upon completion of repeat BVA and upon discharge. See flow chart below (**Table 1**).

Table 1: Patient assessments during the study. SOC indicates standard of care and CS indicates clinical study related procedures.

Required Assessment	Baseline	Day 1	Day 2	Day 3	Day before discharge	Discharge	30 days post discharge
Consent/Randomization	X (CS)						
Medications	X (SOC)	X (SOC)	X (SOC)	X (SOC)	X (SOC)	X (SOC)	X (CS)
Vitals (BP, HR, RR, SpO2, weight)	X (SOC)	X (SOC)	X (SOC)	X (SOC)	X (SOC)	X (SOC)	
Orthostatic vitals	X (CS)				X (CS)	X (CS)	

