Urine output	X (SOC)	X (SOC)	X (SOC)	X (SOC)	X (SOC)	X (SOC)	
Labs: BMP, NT- proBNP, urine sodium, CA-125	X (SOC/CS)	X (SOC/C S)		X (SOC/CS)	X (CS)		
BVA	X (CS)				X (CS)		
Dyspnea Questionnaire	X (CS)	X (CS)	X (CS)	X (CS)	X (CS)	X (CS)	X (CS)
Impedance and lung fluid content measurement	X (CS)				X (CS)	X (CS)	
Echocardiogram	X (SOC/CS)				X (SOC/CS)		
Pulse Wave Analysis	X (CS)				X (CS)		
Physician questionnaire	X (CS)				X (CS)		

Phone Call				Х
				(CS)

Following enrollment, subjects will undergo the following tests/measurements. Some procedures occur as part of standard of care testing (SOC) while some testing will be performed as part of the clinical study (CS). All of the following tests have been approved in the present combination in Pro00100536, PI: [name].

- **IV line** will be placed (SOC)
- If the subject is female and childbearing potential and has not had a **pregnancy test** since the arrival to the hospital, a blood pregnancy test will be done (SOC). If positive the subject will be excluded from the study.
- **Blood work:** Basic metabolic panel (BMP) (SOC), N-terminal pro-brain natriuretic peptide (NT-proBNP) (CS), urine sodium (CS), CA-125 (CS). This will require an extra lab draw. Expected blood loss is <20ml.
- **Blood volume analysis** The described BVA technique is an FDA approved technology for the purpose of volume measurement. It is currently used in clinical practice on patients with syncope, heart failure and sepsis to determine the exact intravascular volume and their components such as plasma volume and red blood cell volume.

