BVA will be completed within 24h of admission and again within 24h before anticipated discharge. Each blood volume analysis will take about 60 minutes to complete. The agent will be delivered to the radiopharmacy and prepared by the radiopharmacy. The agent will be then transported and stored at the DMP/ Radiology. On the study day the agent will be taken from the DMP to the patient's room for the injection. An intravenous line connected to a 50 ml saline solution will be inserted in an arm. This line will be used to inject a small amount of diagnostic radioactive material into the patient's circulatory system. A second IV line will be placed to collect small samples of blood at timed intervals 15 min after injection of drug, then every 6 minutes for an additional 3 samples (18, 24, and 30 minutes). Blood collection timeframes do not have to be exact but time of blood draw will be documented. Approximately 15 ml of blood will be drawn total. The collected blood samples will be processed in the DMP in the device provided by the company.

On the report, values will be expressed as percentage (%) deviation from ideal volumes and the predicted normal BV was determined from patient's height, weight and deviation from ideal body weight. The output on the BVA results will be shared with the clinical teams within an hour of processing as outlined in **Figure 2.** BVA results will be provided only to patients and providers in the unblinded/BVA- guided arm. In the BVA- guided arm the medical team will also be provided with data to inform the medical management of their patients based on observed BVA results (admission and prior to discharge).

The current data supports that ideal patient-specific euvolemic target should be 8-10% above euvolemia. All recommendations will not be binding.

Further, if there is a red-cell deficit of >20% the team in encouraged to consider therapies to augment the red blood cell pool. Treatment is up to the physician discretion.

Similarly, the test might reveal red blood cell overload (polycythemia) which ideally is addressed by the medical team using whatever options are clinically available.

- **Vital Signs:** Recorded vital signs including weight, blood pressure, heart rate, respiratory rate, SpO2
- **Dyspnea questionnaire** using a 7-point Likert scale and Visual Analog Scale (CS)

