- Non-invasive imaging with ultrasound
- Non-invasive hemodynamic monitoring (heart rate variability, Sphygmocor ReDS,

Cardioset)

- Blood volume analysis

10. Risk/Benefit Assessment

This study is associated with only small risks and has the potential to provide significant insight into the physiology of the patient's congestion. Risks are limited to the intravenous line placement, and radiation exposure.

Anticipated benefits to the subject include detailed information on congestion status and extent of fluid overload, otherwise not captured with standard clinical care diagnostic methods. This newly obtained data will be provided back to the patient and provider which then can result in a change in clinical care. However the study or protocol does not have an influence on the clinical care the patient will receive as a result of the newly obtained information.

11. Costs to the Subject

Study-specific activities and assessments will be conducted at no additional cost to the subject. Subjects will still be responsible for standard of care procedures related to hospitalization for heart failure.

12. Data Analysis & Statistical Considerations

Descriptive statistics of continuous outcomes will include sample size, mean, median, standard deviation, minimum and maximum. For categorical outcomes, the number and percentage of subjects in each category will be presented. Statistical comparisons will be made using t-tests for continuous outcomes and chi square or Fisher's exact test (depending on overall event rates) for categorical outcomes.

13. Data & Safety Monitoring

Significant adverse events associated with the study procedures are not expected. 30 day follow-up is planned. Should complications be encountered, they will be reported to the IRB within 10 working days or per IRB policy. The Principal Investigator will also provide an annual report of any side effects or problems to the IRB during the study renewal process.

No protected health information associated with the study procedures will be sent outside of Duke. PHI (subject ID, height, weight, and gender) will be used internally for measuring the blood volume. Additionally, we will capture the birth year of the patient to perform the pulse wave analysis.

14. Privacy, Data Storage & Confidentiality -

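### Section 12 plans only unadjusted t-tests for continuous outcomes although Table 1 already collects baselines; with 50 patients, adjustment is more precise than a final-value t-test once the baseline correlation exceeds about 0.15

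*Combined protocol and SAP*

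**What the plan says.** Section 12 is the whole statistical plan. It lists descriptive statistics and then says: "Statistical comparisons will be made using t-tests for continuous outcomes and chi square or Fisher's exact test (depending on overall event rates) for categorical outcomes". It names no covariate and does not say whether the t-test is applied to the final value or to the change from baseline. No other section adds a model.

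Section 4 has data gathered "upon admission, 24h, 48h, 72h and upon completion of repeat BVA and upon discharge". Table 1 has a Baseline column. Rows such as "Labs: BMP, NT- proBNP, urine sodium, CA-125" and "Impedance and lung fluid content measurement" carry a baseline mark and at least one later mark, as do vitals and weight, BVA, dyspnea, echocardiogram and pulse wave analysis.

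Three further statements in Section 4 matter here. The pilot's main intent is to "gather information on optimal study design, treatment recommendations and sample size for a future planned pivotal trial". On timing, "Upon enrollment patients will be randomized to either the unblinded arm", and "Following enrollment, subjects will undergo the following tests/measurements", so the study baselines come after randomisation. Finally, "The output on the BVA results will be shared with the clinical teams within an hour of processing"; elsewhere Section 4 limits this release to the BVA-guided arm.

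**The concern.** A baseline value of the same measurement usually explains part of the spread in the follow-up value. A t-test on the final value ignores that information. A t-test on the change uses it with a fixed slope of 1, which may be far from the best slope. A linear model with the baseline as covariate estimates the slope from the data and costs one degree of freedom.

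With at most 50 patients, precision is scarce. The planned comparisons may give wider confidence intervals than the collected data allow. In addition, a later trial with a continuous endpoint analysed with adjustment would need the residual SD and the baseline correlation for its sample size. Section 12 plans the ordinary SD but neither of these.

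**Working it through.** **Inputs from the documents.** N=50 (Sections 3 and 4), which Section 6 makes an upper limit; two randomised arms; t-tests for continuous outcomes (Section 12). The plan contains no power or precision figure to reproduce.

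**Assumptions, because the documents are silent.** 25 patients per arm, r from 0 to 0.7, two-sided 5% level, a common slope in both arms, and an illustrative effect of 0.6 follow-up SD. N=30 is shown as a case of incomplete enrollment.

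**Step 1: adjusted model against a final-value t-test.** With the cost of estimating the slope included, the variance ratio is (1 − r²) × (N − 3)/(N − 4). The second factor is 47/46 = 1.022 at N=50 and 27/26 = 1.038 at N=30.

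| r | Ratio, N=50 | Ratio, N=30 |
|---|---|---|
| 0 | 1.022 | 1.038 |
| 0.3 | 0.930 | 0.945 |
| 0.5 | 0.766 | 0.779 |
| 0.7 | 0.521 | 0.530 |

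Setting the ratio to 1 gives a break-even of r = √(1/(N − 3)): √(1/47) = 0.146 at N=50 and √(1/27) = 0.192 at N=30. Allowing also for the slightly larger critical value moves these to 0.150 and 0.201. Simulation at N=50 and r=0.15 gave a variance ratio of 0.999, which is a tie. A 33/17 split gave 0.998, so the threshold hardly depends on the allocation ratio.

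**Step 2: what this means for intervals and power (N=50).** The final-value half-width is t(0.975, 48 df) × √(2/25) = 2.011 × 0.283 = 0.57 SD. The adjusted half-width is t(0.975, 47 df) × √(2/25 × ratio), that is 0.55, 0.50 and 0.41 SD at r = 0.3, 0.5 and 0.7. By the noncentral t distribution, power for a 0.6 SD effect is 55% unadjusted and 58%, 66% and 82% adjusted. At r = 0 adjusted power is 54%.

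**Step 3: adjusted model against a change-score t-test.** With equal SDs at baseline and follow-up, the change score has variance 2(1 − r) relative to the final value: 1.4, 1.0 and 0.6 at r = 0.3, 0.5 and 0.7. The adjusted variance relative to it is 0.930/1.4 = 0.66, 0.766/1.0 = 0.77 and 0.521/0.6 = 0.87. The two are equal at r = 2(N − 4)/(N − 3) − 1, which is 2 × 46/47 − 1 = 0.957 at N=50 and 2 × 26/27 − 1 = 0.926 at N=30. With unequal SDs, where k is baseline SD over follow-up SD, the change factor is 1 + k² − 2rk. Its minimum is 1 − r², at k = r, so the adjusted variance never exceeds the change-score variance by more than 2.2% at N=50 or 3.8% at N=30.

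**Step 4: missing baselines.** At N=50 with baselines missing at random and filled by the overall mean, simulated adjusted power is 57%, 65% and 79% (10% missing) and 57%, 63% and 75% (20% missing) at r = 0.3, 0.5 and 0.7, with type I error of 4.9% to 5.1%. If missingness depends on arm, this protection goes. In a deliberately extreme case (no true effect, the highest 20% of baselines missing in one arm only, overall-mean imputation), type I error is about 6%, 8% to 9%, and 14% to 16% at those r. The spread reflects whether the 20% is a fixed count or a cut-off on the value.

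**The case against.** The strongest reply is that nothing here is an error. The t-test is unbiased in a randomised comparison, power is a weak yardstick for a pilot that states no effect size, and the documents name no pivotal endpoint. Provider choices and 30-day vital status gain nothing from adjustment. All of this stands and limits the point to precision.

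The break-even of 0.15 is also where the gain is zero, not a measure of benefit. The gain is small at r = 0.3 and becomes material from about 0.5, and no r is given. That stands too. It does not favour the t-test, because the loss is capped at 2% to 4% of variance while the possible gain is several times larger.

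As a planning input, r from this pilot will be rough: an observed 0.5 has a Fisher-z 95% interval of 0.26 to 0.68 with 50 patients and 0.17 to 0.73 with 30. This is why r should be reported with its interval.

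The most serious objection concerns the baseline itself. It is taken after randomisation, no statement says that the assignment is concealed at that time, and dyspnea is self-rated. A cut-off at release of the BVA result excludes effects of the result but does not turn the value into a pre-randomisation one. Missing or late baselines could therefore differ by arm, and Step 4 shows that mean imputation would then mislead. A final-value t-test is immune to this. The objection stands as a condition on the remedy, not as a reason to ignore the baseline.

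A reader might infer that the planned analysis is invalid, or that information for the pivotal trial is lost for good. Neither follows: the test is valid, and Section 14 keeps the data for at least six years, so re-analysis is possible.

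**Conclusion.** The point holds as a cheap gain in precision for continuous outcomes with a baseline. With 50 patients analysed, adjustment beats a final-value t-test above r of about 0.15 and, with equal SDs, a change-score t-test below r of about 0.96; with 30 patients these limits are about 0.19 and 0.93. Against a final value, the variance change at N=50 runs from +2% at r = 0 to −7%, −23% and −48% at r = 0.3, 0.5 and 0.7. The arithmetic is firm. The size of the actual benefit is not known, because r is an assumption throughout.

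It would be tempting to read the power figures as the trial's own power, or to widen the point to the choice of visit, patients discharged early, log scaling of biomarkers or repeated-measures models. The documents support neither. They state no effect size or power target, and the further items are either unspecified detail or rest on assumptions about the data. They are not part of this conclusion.

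**What to change.** In Section 12, for each continuous outcome with a baseline, replace the t-test by a linear model of the follow-up value on arm plus the baseline value of the same variable. Report the adjusted difference with its 95% confidence interval, the residual SD, and the baseline correlation with its confidence interval.

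State three safeguards:
- Only baseline values taken before release of the BVA result serve as covariate, with the same time cut-off in both arms.
- The number of missing or late baselines is reported by arm. Overall-mean imputation is used only if missingness is plausibly unrelated to arm.
- The unadjusted t-test is kept as a sensitivity analysis, on the final value so that it does not depend on the baseline.

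The cost is one degree of freedom, recording the time of each baseline measurement in both arms, and slightly more analysis work. No visit, test or patient is added. The imputation rule covers missing baselines only; missing follow-up values remain a separate matter.

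### Section 12 compares continuous outcomes by t-test without using baseline values or baseline BVA, so it can lose precision and gives no estimate of whether the effect of guidance varies with baseline volume

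*Combined protocol and SAP*

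**What the plan says.** Section 12 (Data Analysis & Statistical Considerations) is the whole analysis plan. It lists descriptive statistics, then "Statistical comparisons will be made using t-tests for continuous outcomes", then chi-square or Fisher's exact tests for categorical outcomes. It names no outcome, covariate, model or interaction. It does not say whether a t-test would use the discharge value or the change from baseline.

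Other sections give baseline volume a larger role:

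- Section 3 states that "Knowledge of specific congestion phenotypes will be the basis for targeted treatment algorithms". Its objective B is to "Develop a new BVA-guided treatment algorithm based on the observed experience with BVA at Duke".
- Section 4 gives the pilot's main intent as to "gather information on optimal study design, treatment recommendations and sample size for a future planned pivotal trial".
- Section 4, under blood volume analysis: "BVA will be completed within 24h of admission and again within 24h before anticipated discharge". On the report, "values will be expressed as percentage (%) deviation from ideal volumes". The results are withheld in the standard-of-care arm, so both measurements exist in both arms.
- Table 1 schedules weight, NT-proBNP, lung fluid content and the dyspnea questionnaire at baseline and again later. Urine output and medications are also tracked.

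**The concern.** Two things are at stake.

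The first is precision. If patients differ widely in volume at admission, part of that spread carries through to discharge. A t-test on discharge values leaves it in the error term. A t-test on change removes it fully only if usual care shifts every patient by the same amount. If usual care takes patients part of the way to a target, a change score still carries baseline variation. Regression on the baseline value handles both cases. With about 25 patients per arm, avoidable variance widens every interval carried into pivotal-trial planning.

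The second is a missing estimate. The rationale is that treatment should follow the congestion phenotype, yet each planned comparison gives one average arm difference. How that difference varies with baseline volume would inform the targeted-treatment aim and the design of the next trial. The data for it will be collected, but no analysis of it is planned.

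**Working it through.** **Inputs.** From the documents: N = 50 (Sections 3 and 4) and the stated 8-10% band (Section 4; midpoint 9 used). Assumed, because the documents give none: 1:1 allocation (25 per arm), two-sided 5% level, baseline SD S = 15-25 points of % deviation, residual SD σ = 8, 12 or 16, and an effect of 6 points in the same direction for everyone. N = 50 has no stated derivation, so there is no planning figure to reproduce. Power serves here only to compare methods.

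**Model.** Usual care leaves a fraction k of the gap to target: pre-discharge value = 9 + k × (baseline − 9) + noise of SD σ. The guided arm is the same minus 6. Closing 30%, 40% or 50% of the gap means k = 0.7, 0.6 or 0.5.

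**Within-arm error variance V.**

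- Discharge value: k²S² + σ²
- Change score: (1 − k)²S² + σ²
- Regression on baseline: σ²

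**One case in full (S = 20, k = 0.6, σ = 8).** The variances are 0.36 × 400 + 64 = 208, 0.16 × 400 + 64 = 128, and 64. The standard error is √(2V/25), multiplied for regression by √(1 + 1/46) = 1.011 for estimating one slope. This gives 4.08, 3.20 and 2.29 points. With noncentral t on 48, 48 and 47 df, power for a 6-point effect is 30%, 45% and 73%.

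**All cases, S = 15-25 and k = 0.5-0.7.**

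| σ | Change-score t-test | Regression | Gain (percentage points) |
|---|---|---|---|
| 8 | 29-62% | 73% | 11-44 |
| 12 | 22-37% | 40% | 4-18 |
| 16 | 18-24% | 25% | 1-7 |

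Simulating the same model gives gains of about 11-45, 4-19 and 0-9; the differences at the ends are simulation error.

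**Equal shift.** If usual care lowers everyone by the same amount, the change score and regression both have variance σ². Power is then 74% against 73% (σ = 8), 41% against 40% (σ = 12) and 26% against 25% (σ = 16). Simulation puts the worst cost of adjustment at 1-2 points. The discharge-value t-test has only 12-23% at σ = 8.

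**The same point in correlations, for any outcome with a baseline value.** Regression multiplies the standard error of the discharge-value t-test by √(1 − ρ²) × 1.011, and the change score multiplies it by √(2(1 − ρ)). At ρ = 0.3, 0.5 and 0.7 these are 0.96, 0.88 and 0.72 against 1.18, 1.00 and 0.77. For urine output and diuretic amount, adjusting for baseline BVA cuts variance by r²: 9% if r = 0.3 and 25% if r = 0.5.

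**Precision of the interaction.** Let the baseline mean be μ, set so that 34% lie below 9 (an assumption; z = 0.412, so μ = 9 + 0.412 × S). The 95% half-width of the arm difference at baseline x is t(46) × σ × √(2/25 + 2(x − μ)²/(24S²)). For S = 20, μ = 17.2. At x = 0 and σ = 8 it is 2.013 × 8 × √(0.080 + 0.062) = 6.1 points; at x = 30 it is 2.013 × 8 × √(0.080 + 0.034) = 5.4. Over S = 15-25 the half-widths are 5.8-6.6 and 5.0-6.5. They scale with σ, so they double at σ = 16.

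**The case against.** The case on the other side has five parts.

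*The tests are valid and this is a pilot.* This stands. Simulated type I error with no arm difference is 4.3-5.5% for every method compared, and the protocol makes no power claim. A reader might infer that the t-tests are wrong; they are not.

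*The gain depends on inputs that nobody knows.* This also stands. Residual SD 8 implies a control-arm baseline-to-discharge correlation of 0.68 or more, which may be optimistic, and at SD 16 most of the gain is gone. It is also small if guidance only closes somewhat more of the gap than usual care does. With 30% closed under usual care and 50% under guidance, at residual SD 8, a change-score t-test has 6-9% power and regression 8-14%; with 40% and 50%, it is 5-6% and 5-8%. Section 12 does not exclude a change score. What survives is the asymmetry: adjustment costs almost nothing where it does not help.

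*An interaction cannot be tested usefully at N = 50.* Correct. With a 34%/66% split, power is about 26% for a subgroup difference of 0.8 SD, and the half-widths above are about as large as the assumed effect. This argues for an estimate with an interval, not for leaving it out.

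*Objective B does not require an interaction estimate.* Fair. It rests on observed experience, and the physician questionnaire feeds it directly. The estimate would inform the aim; the documents do not make it a condition.

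*A stronger reading is tempting.* Section 4 says "ideal patient-specific euvolemic target should be 8-10% above euvolemia". A reader might infer that guidance moves patients above and below the target in opposite directions, so that the arm means cancel. The documents do not support this as a finding. "All recommendations will not be binding", the visible text gives no rule for patients below target, and Figure 2 is not shown. The 34% in Section 2 is the hypovolemic-or-euvolemic share, not the share below 8-10%. Adjusting a signed mean would not cure such cancellation in any case: under one such scenario, power stays at 5-7% with or without adjustment.

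**Conclusion.** The point holds as a cheap improvement to a valid but thin analysis plan. Section 12 makes no use of baseline values that the trial already collects, and it gives no estimate of how the effect of guidance varies with baseline volume. The direction is secure: under the model used, baseline adjustment is never worse than a change-score t-test by more than about 1-2 points of power. The size is not secure. The gain of about 11-45 points at residual SD 8 falls to 4-19 at SD 12 and 0-9 at SD 16. Every figure also rests on the assumed baseline SD of 15-25, the 6-point same-direction effect and 25 patients per arm. Cancellation of opposite effects is conjecture and forms no part of this conclusion.

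**What to change.** In Section 12:

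1. Name the continuous outcomes. Where an outcome has a baseline value (pre-discharge blood volume % deviation, weight, NT-proBNP, lung fluid content, dyspnea scores), compare arms by linear regression adjusted for that outcome's own baseline. For urine output and diuretic amount, adjust for baseline BVA % deviation.
2. For blood volume and the treatment-intensity outcomes, report the interaction of arm with continuous baseline BVA as an exploratory estimate with a 95% CI, for example as arm differences at two stated baseline values. Say that it is not a powered test. Define the covariate as the baseline BVA taken before any result is disclosed, because Table 1 puts randomization and the first BVA in the same baseline column.
3. Keep the unadjusted arm means as a summary.
4. Optionally, report distance of pre-discharge blood volume from the stated 8-10% band, adjusted for baseline distance. Label it an exploratory measure of uptake of advice, since only guided teams see the result.

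The cost is a few sentences and a little more analysis work, with no new visits, tests or patients. The downsides are wide interaction intervals at N = 50, and little or no gain over a change-score t-test if usual care shifts everyone equally or residual noise is large.
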